1. **Arm 1: Standard of Care - Plus (SCP) Comparator Intervention: BP Training, HTN Education, and Audit/Feedback.** Consistent with our conceptual model, practices in the comparator group are receiving an audit, feedback and education intervention that targets the health system overall (designated practice champion leadership support for improvement); the delivery system (evidence-based training to improve BP measurement, improve HTN care and overcome practice inertia for providers and staff); and the clinical information system (feeding back HTN control performance at practice and provider levels). This multi-level strategy is designed to reinforce and standardize evidence-based HTN care practices across intervention and comparator practices. SCP is being implemented at half of the practices. SCP includes audit and feedback using a HTN dashboard and a linked educational intervention. The latter aims to: 1) standardize BP measurement technique and 2) enhance provider and staff awareness of evidence-based approaches to overcome practice inertia, improve follow-up, and engage patients in self-

care. Our goal is to integrate audit and feedback of HTN control performance, proper BP measurement techniques, and HTN care best practices as “usual care” at each practice. Each practice is required to have capacity to generate reports on HTN control rates by practice and provider using EMR data and to identify a practice champion (usually a physician) to lead the audit, feedback, and education intervention implementation. Education for all staff on proper BP measurement technique is also featured in this study arm. Practice champions receive support for facilitating: 1) distribution of feedback reports; 2) delivery of training on BP measurement technique and evidence-based strategies to improve HTN care and control, and 3) standardized BP measurement with automated BP measurement devices for screening and confirmatory measurement. Many of the materials provided to practice champions are adapted from previously developed materials and given to practice teams in both interventions (see Table 5 below). The interventions given to this arm are:

- i. BP Measurement Training
- ii. HTN Care and Control Best Practices Training
- iii. HTN Dashboard
- iv. System Level Leadership Intervention

Table 5: Tools available to Practice Level Champions, Providers, and Staff in Both Interventions

| Category | Tool/material name | Description |
|--|--|--|

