A periodically updated blog shares information with practices on a variety of topics. Practice champions are encouraged to print and share information with their teams. Current and future content may include (1) Written or video responses to practice questions about the protocol and OMRON, (2) reinforcement of proper BP measurement technique, (2) examples of successful site HTN care improvement strategies, (3) HTN treatment guideline updates, and (4) summary of recently published HTN research that may influence treatment decisions.

Section 6C: Interventions Description: HTN Dashboard-Audit/Feedback

1. **Rationale:** Transparent and timely access to and review of clinical performance data are among the key elements of successful improvement activities. For this reason, our study provides access to practice- and physician-level data through the study dashboard. Data is uploaded to the clinical dashboard and new reports generated quarterly. Reports display data from the previous 3 months.
2. **Description of the Dashboard and instructions regarding its use:**
 - a. **Dashboard (for both SCP and CC/Stepped Care):**
 - i. The Practice Dashboard provides a display of percentage of patients achieving BP control, defined as <140/90 mm Hg for the overall practice.
 - ii. The Provider Dashboard provides a display of percentage of patients achieving BP control, defined as <140/90 mm Hg for each provider's patient panel.
 - iii. Both the Practice and Provider Dashboards break down hypertension performance by race (White, non-Hispanic; Black, non-Hispanic; and All Hispanic).
 - iv. Specific instructions, or dashboard logic, for generating reports will be provided to each health system's clinical IT team.
3. **SCP Arm specifics**
 - a. **Providers**
 - i. Reports providing an overview of overall practice performance data are available quarterly through the project dashboard. Health systems notify providers following each dashboard update. Providers are encouraged to review the hypertension dashboard quarterly to obtain a snapshot of their progress in meeting the practice's goals.

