|--|---------------------|---------------------|
| Body mass index | EMR | EMR |
| Healthcare and Prescription Drug Utilization | | |
| Healthcare insurance status | Telephone Interview | Telephone Interview |
| Hospitalizations, ED use, 30-day Readmissions | Claims | Claims |
| Prescription refills and medication possession ratios for relevant medications | | |
| Social and Demographic Measures | | |
| Age, Gender, Ethnicity/Race, Primary Language, Employment, Insurance, Income, Wealth, Disability* ^{141,148} | Telephone Interview | Telephone Interview |
| Health Literacy (CHEW) | | N/A |
| Subjective Numeracy (Three-Item Subjective Numeracy Scale) | | |
| Life Events | | |
| Everyday Discrimination | | |
| Community Stressors: Violence | | |
| Community Stressors: Total Victimization | | |
| Community Stressors: Disorder | | |
| Adverse Childhood Experience (ACE) Questionnaire | | |
| Emotional support (PROMIS Social Functioning Scale) ¹⁴⁹ | N/A | Telephone Interview |
| Informational support (PROMIS Social Functioning Scale) ¹⁴⁹ | | |
| Instrumental support (PROMIS Social Functioning Scale) ¹⁴⁹ | | |
| Family composition and spillover | | |
| Abbreviations: CHW, Community Health Worker; PHQ, Patient Health Questionnaire. *Collected at baseline only +Collected for patients in CC/Stepped Care only | | |

Table 13: Study Measures (Provider, Practice, and System Levels)

| | Baseline | Follow-Up |
|---|------------------------------|------------------------------|
| Provider and Staff Level Variables | | |
| Sources | | |
| Age, Gender, Race/Ethnicity, Education, Professional Role, Years of Experience | Online Survey | Online Survey |
| Cultural competence, Patient-centeredness (PPOS) ^{152,153} | | |
| Perceptions of practice quality improvement capacity, ¹⁵⁴ patient-centeredness, ¹⁵⁵ cultural competency and barriers to addressing health disparities, ¹⁵⁶ teamwork ¹⁵⁷ | | |
| Provider and staff knowledge assessments | | |
| Practice Level Variables | | |
| Number and types of clinicians and staff, practice type (private, FQHC); resources | Survey | |
| Patient-level outcomes averaged across all patients from the site | EMR, Interview | EMR Telephone |
| System-Level Variables | | |
| System values, priorities, and capacity for change, leader attitudes | Survey, In-person interviews | Survey, In-person interviews |

D. System-Level Leadership measures

Table 14: Provider Measures

| Variable type | Items | Measurement tool | Platform |
|--|--|---|--|

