We will use descriptive statistics to characterize the organizations, providers, and patients, using means and standard deviations, medians and interquartile ranges, or frequencies and percentages where appropriate. Descriptive statistics of central tendency and variability will be generated for outcomes. The distributions of each continuous outcome variable will be assessed for normality, and appropriate transformations will be made if necessary. Two-sample t-tests, Wilcoxon rank-sum tests, and Fisher’s exact test will be used to compare baseline demographic and practice characteristics across intervention arms.

Primary statistical analyses testing the differences in outcome (or change in outcome over time) between intervention groups will be conducted using the intention-to-treat principle. For our clinical outcomes at our primary endpoint of 12 month follow-up, we will select the EMR measure that is closest to 12 months following the baseline survey (enrollment date) for each patient as long as it is within the 6 month window.

General Approach

These analyses will utilize all available data through modeling approaches for correlated outcomes. All missing data will be assumed to be missing at random (MAR) conditioning on the observed data, and models will be adjusted for characteristics associated with missingness and key variables not balanced by the cluster randomization. In sensitivity analyses, missing data will be imputed using likelihood based longitudinal models developed under the MAR assumption. Missing data under plausible informative missing scenarios will be multiple-imputed using these likelihood based models with the mean models tuned according to the plausible informative missing scenarios. These sensitivity analyses will verify the robustness of the results derived under MAR assumption. All tests will be two-sided and significance will be set at $\alpha < 0.05$. Analyses will be conducted using SAS version 9.4 or higher (SAS Institute, Inc., Cary, NC) or Stata SE14 or higher (StataCorp, College Station, TX).

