We will use mixed-effects regression models for continuous outcomes and Generalized Estimating Equations (GEE) analysis for dichotomous outcomes. For mixed-effects regression modeling, we will assume an unstructured correlation structure for longitudinal analyses of outcomes with repeated measurements over time, employ random effects to address clustering by practices, include appropriate covariate adjustment in the fixed effects, and use robust estimates for statistical inferences. The GEE approach is robust to outcome correlation misspecification, so we will just assume an exchangeable correlation structure for the outcomes, include appropriate covariates in the mean model, and use robust estimates for statistical inferences. We will use mixed-effects regression models under the MAR assumption as the basis to conduct multiple imputation for missing BP data or other outcomes as appropriate. In sensitivity analyses evaluating potential impacts under sensible informative missing

(NMAR) scenarios, we will preserve the mixed-effects regression based variance-covariance estimates, and manipulate the mean model under each informative missing scenario to carry out multiple imputation. Missing binary outcomes (e.g., controlled BP or lipids) will be derived based on multiple-imputed continuous values using appropriate observed data likelihood models as described.

Statistical analysis plan for primary outcomes

For the primary clinical outcome of BP control at 12 months we will model the binary variable BP controlled (yes/no) at 12 months using GEE with a logit link on the intervention arm indicator (CC/Stepped Care arm vs. SCP arm). Additional covariates will be included as appropriate as described previously, including appropriate cluster level characteristics and variables associated with occurrence of missing data. With correctly specified mean model, the GEE is robust to misspecification of correlation structure so the statistical inferences will account for outcome correlation due to patients clustering within practice and be valid under MCAR. The regression coefficient for the intervention arm indicator estimates the log-odds ratio of BP control at 12 months for the CC/Stepped Care arm to the SCP arm. Multiple imputation of missing BP outcomes will be carried out to impute the missing BP control outcomes to produce proper inferences under MAR and to conduct sensitive analyses under NMAR scenarios.

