For the CC/Stepped Care arm, exploratory analysis will be conducted to determine which parts of the intervention, e.g., number of CM and CHW contacts, were more successful in improving BP control and reducing systolic BP, or if there was an overall “dose” effect.

Power calculation

We aim to recruit a total of $n=1,890$ unique patients. We planned for 20% random attrition which would yield an analytic sample of 1,500 (effective size of 50 patients per practice).^{104,105} A review of cluster-randomized trials in primary care found a median intracluster correlation coefficient (ICC) of 0.04, with an interquartile range of -0.02 to 0.21.¹⁶⁴ Assuming a 5% ICC, 15 clusters of 50 patients per intervention arm and a two-sided alpha of 0.05, we will have 80% power to detect a difference in proportion of patients with BP controlled of 11-13% (depending on whether the proportion controlled in the SCP arm is 50%-70%). With the same assumptions and sample size, using a two-sample t-test, we will be able to detect an effect size of 0.278. Operationalizing this for the primary and important secondary outcomes, we anticipate that for PAM-13, estimating a $SD=10.0$,¹⁶⁵ we would be able to detect a mean difference of 2.78 between the CC/Stepped Care and SCP arms; for systolic BP, estimating a $SD=19.5$ mm Hg,¹⁵³ we could detect a mean difference of 5.42 mm Hg between the CC/Stepped Care and SCP arms.

Design Considerations:

Participants will be considered to be enrolled at the time they are given their randomization assignment, which will occur at the end of the baseline interview. Data from all enrolled participants will be analyzed as intent-to-treat.

Missing Data

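### The primary BP-control model names no practice-level baseline covariate; fixing the practice's pre-intervention control rate in advance would be a cheap gain in precision if that rate predicts outcome

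*Combined protocol and SAP*

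**What the plan says.** Section 8, statistical analysis plan for primary outcomes, defines the main analysis of 12-month BP control: "we will model the binary variable BP controlled (yes/no) at 12 months using GEE with a logit link on the intervention arm indicator". The next sentence opens the model to more terms: "Additional covariates will be included as appropriate as described previously, including appropriate cluster level characteristics and variables associated with occurrence of missing data". The general rule it refers back to, under General Approach, is that "models will be adjusted for characteristics associated with missingness and key variables not balanced by the cluster randomization". No covariate is named in any of these places. The 24-month GEE uses the same open wording.

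The power calculation contains no covariate. Its inputs are given as "Assuming a 5% ICC, 15 clusters of 50 patients per intervention arm and a two-sided alpha of 0.05". From these it reports a detectable gap in BP control of 11 to 13 percentage points at 80% power, and a detectable standardised effect of 0.278.

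Three places bear on a practice-level control rate. Section 6B (Arm 1) says "Each practice is required to have capacity to generate reports on HTN control rates by practice and provider using EMR data". Section 6C (HTN Dashboard) says, for both arms, "The Practice Dashboard provides a display of percentage of patients achieving BP control, defined as <140/90 mm Hg for the overall practice", updated quarterly with a three-month look-back. Section 7B plans to collect common EMR metrics for all practices from the networks' central offices. The practice-level part of Table 13 also lists "Patient-level outcomes averaged across all patients from the site", with EMR and interview as baseline sources.

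**The concern.** Practices are the randomised units, 15 per arm, so differences between practices drive the standard error of the arm comparison. A baseline version of the outcome is usually the best single covariate for reducing that error. The PAM-13 and systolic BP models contain the baseline measurement. The binary primary model has no counterpart: Table 3 requires systolic BP of at least 140 mm Hg, and Section 5E makes that reading the baseline BP in both arms, so baseline control is constant at zero among participants. The practice's control rate over its whole hypertensive panel does vary and uses the same 140/90 threshold.

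The stated selection rules would reach this variable only if it happened to be imbalanced or related to missing data. Neither rule picks a covariate because it predicts which practices control BP well, and both are applied after data have been seen. What is at stake is power for the clinical primary outcome, and a covariate list still open for the primary test.

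**Working it through.** **Inputs from Section 8, power calculation:** ICC 0.05; 15 practices of 50 patients per arm; two-sided alpha 0.05; effect size 0.278. **Assumption, not in the documents:** r, the correlation between a practice's pre-intervention control rate and its underlying 12-month control level, taken from 0 to 0.7.

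**1. Reproduce the plan.** Design effect = 1 + 49 × 0.05 = 3.45; effective n = 750 / 3.45 = 217.4 per arm. With 28 df (30 practices − 2), the detectable effect is (t₀.₉₇₅ + t₀.₈₀) × √(2/217.4) = 0.278, as stated. For proportions (normal reference) the detectable difference is 13.3 points from an SCP rate of 50% and 11.5 from 70%, agreeing with the stated 11–13.

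**2. Share of variance between practices.** In SD units, the variance of a practice mean is v₀ = 0.05 + 0.95/50 = 0.069. The between-practice share is 0.05/0.069 = 72%. It changes with the ICC: 51% at 0.02, 68% at 0.04 (the median the plan cites), 85% at 0.10, 93% at 0.21 (the cited upper quartile). It vanishes as the ICC approaches 0, which the cited interquartile range includes.

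**3. Effect of a practice-level covariate.** The variance becomes v(r) = 0.05 × (1 − r²) + 0.019. At r = 0.5, v = 0.0565 and the SE ratio is √(0.0565/0.069) = 0.905, before the cost of estimation.

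**4. Cost of estimating the slope.** One df is lost (27 left). In addition, chance correlation R between arm and covariate across 30 practices inflates the variance of the arm effect by 1/(1 − R²), which averages 1 + 1/26 = 1.038 for a normally distributed covariate. Power was taken from the noncentral t at effect 0.278, SE = √[2v(r)/15/(1 − R²)], averaged over random draws of the covariate.

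| r | v(r) | Power, 1 df charged only | Power, chance correlation included |
|---|---|---|---|
| no covariate | 0.0690 | – | 79.9% (28 df) |
| 0 | 0.0690 | 79.8% | 78.4% |
| 0.2 | 0.0670 | 80.9% | 79.5% |
| 0.3 | 0.0645 | 82.4% | 81.0% |
| 0.4 | 0.0610 | 84.4% | 83.1% |
| 0.5 | 0.0565 | 87.0% | 85.8% |
| 0.7 | 0.0445 | 93.5% | 92.7% |

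The last column is the one to use. Break-even is near r = 0.25.

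**5. Check on the proportion scale.** A cluster-level simulation (control rate 50%, ICC 0.05, 15 × 50 per arm, 6,000 runs per r) gave adjusted-to-unadjusted SE ratios of 1.01 at r = 0, 0.98 at 0.3, 0.93 at 0.5 and 0.83 at 0.7. At r = 0.5 the detectable difference from 50% would be roughly 13.3 × 0.93 = 12.4 points.

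**6. Sensitivity to the ICC.** At ICC 0.02, unadjusted power for effect 0.278 is already about 96%, and r = 0.5 adds only about 1 point. These are linear cluster-level approximations to the planned logit GEE.

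**The case against.** A reader who stops at the first sentence of the model might infer that the plan excludes this covariate. It does not. The following sentence admits appropriate cluster-level characteristics, a category wide enough to hold a practice control rate. The variable is unnamed, not left out.

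A reader might also infer that the rate already exists for all 30 practices. The documents do not show that. Section 6B requires reporting capacity; the dashboard is itself an intervention component in both arms; Section 7B does not name the control rate among its metrics. The Table 13 row may be an average over enrolled patients, since interview data exist only for them, and their baseline control is constant. The rate is derivable, and no more than that.

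The benefit rests on an unknown r. Participants are selected as uncontrolled, by preference at highest risk, and sampled by race and ethnicity, so a whole-panel rate may only weakly predict how many of them reach control. The relevant r is also what remains after any other practice-level adjustment. Other practice variables, such as network, case mix or mean baseline systolic BP, might explain some of the same variance.

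Randomisation was stratified by practice network and blocked, and imbalanced key variables are to be adjusted for, so chance imbalance is not unguarded. These safeguards do not balance practices on hypertension performance within a network, and adjustment triggered by imbalance is not designed for precision.

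All of this limits the size of the point. What remains is that no predictive practice-level covariate is fixed in advance for the primary test.

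**Conclusion.** This is a cheap improvement. The primary BP-control model has no informative baseline of its own outcome, the planned selection rules do not look for one, and at the planning ICC about 72% of the variance of a practice mean is of the kind that only variables differing between practices can explain. A pre-specified practice control rate would change power from 79.9% to about 81.0–85.8% for r between 0.3 and 0.5 and to about 92.7% at r = 0.7. It would cost up to about 1.5 points if the rate carries no information. These figures assume ICC 0.05, 50 analysed patients per practice, one practice-level covariate and an r that the documents do not supply; at a lower ICC the gain shrinks.

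Two stronger conclusions might be drawn and are not supported. The stated power figures are not wrong: they assume no adjustment and reproduce on that basis. Nor is bias shown: the randomised comparison is valid without this covariate.

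**What to change.** In Section 8, name one fixed practice-level covariate in the 12-month BP-control GEE and in the joint 12- and 24-month GEE: the practice's percentage of hypertensive patients with BP below 140/90. Take it from a fixed EMR window after the BP devices and training are in place and before the dashboard and the arm-specific interventions begin at that practice. Section 6C (BP Measurement Training) puts device introduction and training at least three months before the collaborative and stepped care roll-out, so such a window should exist; its end must also precede the dashboard. Include the covariate whatever its observed balance, and show the model without it as a sensitivity analysis. State the remaining covariates as a closed list.

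The cost is SAP wording, one variable per practice, one of 28 df, and the power loss of up to about 1.5 points if r is near zero. First confirm that the rate can be extracted for all 30 practices, including the replacement practices. Where no usable report exists, derive it from the practice's EMR data with the same window and definition. If pre-intervention EMR data allow r to be estimated without reference to trial outcomes, do that before fixing the covariate.

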For the primary patient-reported outcome of change from baseline in PAM-13 score at 12 months, we will model the baseline and 12-month PAM-13 measurements using a mixed-effects linear regression model, with the intervention arm indicator (CC/Stepped Care arm vs. SCP arm), 12-month time indicator, and the cross-product term of intervention by time interaction as the fixed mean effects, the practice indicator as a random effect, and additional covariates included as fixed effects as appropriate as described previously. The fixed effect regression coefficient for the cross-product term of intervention by time estimates the mean difference of 12 month change in PAM-13 between arms.

Statistical Analysis Plan for Secondary Outcomes

For the outcomes of systolic and diastolic BP measures at 12 months, we will select the blood pressure measure that is closest to 12 months of follow-up for each patient as long as it is within the 6-month window (either direction). We will model the baseline and 12-month BP measurements using a mixed-effects linear regression model, with the intervention arm indicator (CC/Stepped Care arm vs. SCP arm), 12-month time indicator, and the cross-product term of intervention by time interaction as the fixed mean effects, the practice indicator as a random effect, and adjusting for additional covariates as fixed effects as described previously. The random effect for the cluster ID will be used to capture the outcome correlation for patients nested within the cluster. The fixed effect regression coefficient for the cross-product term of intervention by time estimates the mean difference of 12 month change in BPs between arms.

For the other secondary measures, e.g., laboratory measures of hemoglobin A1c and lipids, we will use methods similar to the assessment of 12 month outcomes for blood pressure, i.e., select the within window measure in the EMR closest to 12 months after baseline and use mixed-effects linear regression or GEE models to assess the outcomes while controlling for outcome clustering within practice.

Subgroup and Exploratory Analyses

Durability of intervention effect at 24 months

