For the Patient Survey (telephone interview) data: To limit missing data at baseline, we are not considering the patient to be enrolled in the study until they complete the baseline survey. We make the participant fully aware of the time involved to complete the survey prior to beginning. We also give the participant the option to complete the survey in more than one telephone call. Our interviewers are trained to encourage the participant to complete the entire survey. Though the participant may choose not to answer some of the questions, we are requiring that they answer at least 10 items of the PAM-13 since this is a primary outcome. Participant data entered into REDCap will be reviewed weekly by the data manager for completeness. If data were inadvertently missing (the participant did not refuse to answer), the interviewer will be asked to re-contact the participant to obtain these data. If there are patterns of missing data across interviewers, we will work to identify why this is occurring and modify training, as necessary, to correct the issue. We are using the scheduling system within REDCap to track when participants are due for follow-up telephone surveys. Additionally, if patients are still being seen at the participating health system, we will have access to updated telephone numbers and addresses. We have tried to minimize study participant burden and follow-up interviews should take less time to complete than the baseline. We will seek to replace dropout patients with others from the same clinic when these occur early in the intervention period. A dropout is defined as any participant who, after completing the baseline survey and receiving their randomization assignment, states that s/he wants to withdraw from the study and receive no further contact from the study team. If this occurs within two (2) months of the date of randomization, we will attempt to recruit an additional patient from the same practice.

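### PAM-13 and blood pressure effects are estimated as raw differences in mean change without adjusting for the baseline value: valid, but less precise than the collected data allow, and the power text does not say which SD it uses

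*Combined protocol and SAP*

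**What the plan says.** Section 8, plan for primary outcomes: "we will model the baseline and 12-month PAM-13 measurements using a mixed-effects linear regression model, with the intervention arm indicator", a 12-month indicator and their product as fixed effects, and practice as a random effect. The effect is read from the product term: "cross-product term of intervention by time estimates the mean difference of 12 month change in PAM-13 between arms".

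Section 8, plan for secondary outcomes, has the same structure: "We will model the baseline and 12-month BP measurements using a mixed-effects linear regression model", and again "cross-product term of intervention by time estimates the mean difference of 12 month change in BPs between arms". Change in systolic BP is named there as the leading secondary clinical outcome.

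On covariates, the General Approach says only that "models will be adjusted for characteristics associated with missingness and key variables not balanced by the cluster randomization". The outcome's own baseline is not named.

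Baseline values are secured by design. Section 5E makes PAM completion a condition of enrolment and takes the qualifying BP as the baseline BP. The Missing Data text adds: "we are requiring that they answer at least 10 items of the PAM-13 since this is a primary outcome".

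The power calculation rests on 15 practices of 50 patients per arm, ICC 0.05, two-sided alpha 0.05 and 80% power: "using a two-sample t-test, we will be able to detect an effect size of 0.278". It converts this to 2.78 PAM-13 points (SD 10.0) and 5.42 mm Hg (SD 19.5). It gives no within-patient correlation and does not say whether either SD is of the score or of the change.

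**The concern.** With a free arm main effect, the arms may have different baseline means, and in complete data the interaction is simply the difference between the arms in mean change. A change score subtracts the whole baseline value, noise included. Regression on baseline subtracts only the predictive part, so with many practices it is at least as precise. The number of practices is fixed at 30, so precision already available in the data is worth taking for a primary outcome.

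The power figures also appear to describe a third estimator, a comparison of one measurement per patient. If so, they show neither what the planned change contrast can detect nor what an adjusted analysis could.

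**Working it through.** **1. The plan's figure.** Design effect 1 + (50 − 1) × 0.05 = 3.45. Effective patients per arm 750 / 3.45 = 217.4. With 28 df (30 practices − 2), (2.048 + 0.855) × √(2 / 217.4) = 0.2784. Then 0.278 × 10.0 = 2.78 and 0.278 × 19.5 = 5.42. The stated figures reproduce for a cluster-corrected t-test on one measurement.

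**2. The planned coefficient.** In complete simulated data with a practice random intercept, the arm-by-time coefficient and the raw difference in mean change were both 2.3549.

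**3. PAM-13, equal SDs.** Variance relative to a follow-up-only comparison:

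- change: 2(1 − R)
- baseline-adjusted: 1 − R²
- ratio, change to adjusted: 2 / (1 + R)

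For practice means of m patients, R = [m × ICC × c + (1 − ICC) × τ] / [1 + (m − 1) × ICC], where c is the practice-level and τ the patient-level correlation between baseline and 12 months. Neither is in the documents. I assume τ = 0.5 and c = 0.3, 0.5, 0.8:

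- (2.5 × 0.3 + 0.475) / 3.45 = 0.36
- (2.5 × 0.5 + 0.475) / 3.45 = 0.50
- (2.5 × 0.8 + 0.475) / 3.45 = 0.72

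Multiplying 2.784 (0.2784 × 10.0) by the square root of each factor, with unrounded R:

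| R | Change (planned) | Baseline-adjusted | Variance ratio |
|---|---|---|---|
| 0.36 | 3.16 | 2.60 | 1.48 |
| 0.50 | 2.78 | 2.41 | 1.33 |
| 0.72 | 2.09 | 1.94 | 1.16 |

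Power for 2.78 points, change against adjusted: about 66% and 83% at R = 0.3; 80% and 90% at R = 0.5; 95% and 97% at R = 0.7.

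**4. Only 30 practices.** The formula ignores the cost of estimating the baseline slope. In a simulation of 30 practices (ICC 0.05, adjustment for practice-mean baseline), the adjusted-to-change variance ratio was 0.66, 0.78, 0.90 and 0.96 at R = 0.30, 0.50, 0.75 and 0.85. The formula (1 + R)/2 gives 0.65, 0.75, 0.87 and 0.92. Adjustment was more precise each time, by slightly less than the formula says.

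**5. Systolic BP.** The baseline is the qualifying reading, at least 140 mm Hg, so the baseline and 12-month SDs (s0, s1) differ. The change variance is s0² + s1² − 2R·s0·s1, the adjusted variance is s1²(1 − R²), and change equals follow-up-only at R = s0 / (2·s1), not at 0.5.

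I assume a normal source population with SD 19.5 and untruncated correlation ρ. For source mean 140 and ρ = 0.5: s0 = 11.75, s1 = 17.88, R = 0.329. The change SD is 17.88 and the adjusted SD 16.89, so the variance ratio is (17.88 / 16.89)² = 1.12. Detectable differences, carrying 0.2784 over, are 4.98 and 4.70 mm Hg. At the edges of the assumed range:

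| Source mean | ρ | Change SD | Adjusted SD | Variance ratio | Detectable: change | Detectable: adjusted |
|---|---|---|---|---|---|---|
| 130 | 0.3 | 19.89 | 18.60 | 1.14 | 5.54 | 5.18 |
| 130 | 0.7 | 14.25 | 13.93 | 1.05 | 3.97 | 3.88 |
| 145 | 0.3 | 20.61 | 18.60 | 1.23 | 5.74 | 5.18 |
| 145 | 0.7 | 14.44 | 13.93 | 1.07 | 4.02 | 3.88 |

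Across means 130 to 145 and ρ 0.3 to 0.7, break-even R runs from about 0.27 to 0.38. These are patient-level figures with the 3.45 design effect carried over unchanged.

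**The case against.** The declared outcomes are changes from baseline, and the interaction estimates exactly that. This stands: nothing is biased, and the choice concerns efficiency.

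The SAP also says "we will assume an unstructured correlation structure for longitudinal analyses of outcomes with repeated measurements over time". That lets baseline inform patients without a 12-month value, but in complete data it leaves the interaction equal to the raw difference in mean change. The covariate clause does not supply the adjustment either: it covers imbalance and missingness, and the baseline is already part of the outcome vector.

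Four stronger readings are tempting, and the documents do not support them.

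- *The detectable differences are wrong or will be missed.* The arithmetic is right. If 10.0 and 19.5 are SDs of change, 2.78 and 5.42 fit the planned estimator. If they are SDs of the score, 2.78 is optimistic for PAM-13 change only when R is below 0.5. Systolic BP change gives about 4.0 to 5.7 against 5.42, so most of that range meets the plan.
- *The entry cut-off makes the BP change score much worse.* It lowers R, but it also shrinks the baseline variance that a change score adds. The equal-SD ratio does not apply, and the penalty is small. Section 8 also plans normality checks, transformations and robust inference.
- *Dropping the arm main effect is the same repair.* Health systems learned their allocation in March 2017 (Section 3G), recruitment began in August 2017 (Section 5D), and a replacement practice took the lost practice's arm (Section 4D). Patients were surveyed before learning their arm, but a common baseline mean still needs an argument.
- *A model of 12-month values costs no patients.* Without imputation it drops those with no 12-month value, against a planned 20% attrition.

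**Conclusion.** The point holds as one of efficiency and of consistency between the analysis and power sections. For PAM-13, with equal SDs and R of 0.36 to 0.72, the planned contrast has 1.48 to 1.16 times the variance of a baseline-adjusted one, somewhat less with 30 practices. The gain fades as R approaches 1. For systolic BP the ratio is about 1.05 to 1.2 under the assumed source population. No diastolic figure can be given, because the documents state no diastolic SD. R is assumed throughout, so these are ranges. Whether 2.78 and 5.42 suit the planned contrast depends on which SD is meant, and only the sponsor can say. The change is worth making for a primary outcome because it is nearly free and settles the choice of estimator in advance.

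**What to change.** In Section 8, make the main analysis of 12-month PAM-13, systolic BP and diastolic BP a mixed model with arm, the patient's own baseline value and, if wanted, the practice-mean baseline as fixed covariates, and practice as a random effect. Use the multiple imputation already planned for missing 12-month values. Subtracting baseline from both sides leaves the arm coefficient unchanged, so it is still a difference in 12-month change, adjusted for baseline. The arm-by-time model can stay as a sensitivity analysis. If a longitudinal model with equal baseline means is preferred, state why that constraint is credible given recruitment after randomisation.

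In the power section, say whether 10.0 and 19.5 are SDs of the score or of the change. If of the score, say that 2.78 and 5.42 mm Hg assume a single-measurement comparison. They are then conservative for the adjusted analysis and, for the planned PAM-13 change contrast, optimistic if R is below 0.5. Restating them for the chosen estimator with an assumed R is better still.

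The cost is SAP wording, with no new data.
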